9.2 Pharmacokinetic Analysis

Final PK calculations will be performed using appropriate software, e.g., PhoenixTM WinNonlin[®] (Version 8.1 or higher, Certara, L.P. in conjunction with the internet-accessible implementation of Pharsight[®] Knowledgebase ServerTM [PKSO; Version 4.0.4 or higher, or comparable product, Certara, L.P.]) and/or SAS[®] (Version 9.4 or higher, SAS Institute Inc.).

PK parameters will be calculated using non-compartmental analysis. The following PK parameters will be determined as appropriate for each study part and analyte.

AUC _{Extrap} (%)	The percentage of extrapolated AUC to AUC _{inf} based on extrapolation (Parts 1 and 3)
AUC _{inf}	Area under the concentration-time curve from time-zero extrapolated to infinity; calculated for Parts 1 and 3 as: $AUC_{inf} = AUC_{last} + \frac{C_{last}}{\lambda_z}$
AUC _{last}	Area under the concentration-time curve from time-zero to the time of the last quantifiable concentration; calculated using the linear trapezoidal rule (Parts 1 and 3)
AUC _{tau}	Area under the concentration-time curve during the dosing interval; calculated using the linear trapezoidal rule (Part 2)
C_{avg}	Average concentration during the dosing interval (Part 2)
C _{last}	The last quantifiable concentration determined directly from individual concentration-time data (Parts 1, 2, and 3)
CL/F	Apparent total clearance after single administration (Parts 1 and 3)
CLss/F	Apparent total clearance after multiple administration (Part 2)
C _{max}	Maximum concentration, determined directly from individual concentration-time data (Parts 1, 2, and 3)
R _{AUC}	Accumulation factor during multiple dosing, based on AUC _{tau} (Part 2)
R _{Cmax}	Accumulation factor during multiple dosing, based on C _{max} (Part 2)
T _{last}	Time of the last quantifiable concentration (Parts 1, 2, and 3)
T _{max}	Time of the maximum concentration (Parts 1, 2, and 3)
T _{1/2}	The observed terminal half-life, calculated for Parts 1, 2, and 3 as: $T_{1/2} = \frac{\ln(2)}{\lambda_z}$
Vz/F	Apparent volume of distribution in the terminal phase (Parts 1, 2, and 3)

 λ_{z}

The observed terminal rate constant; estimated by linear regression through at least 3 data points in the terminal phase of the log concentration-time profile (Parts 1, 2, and 3)

Additional PK analysis and modeling with multiple compartment model may be performed and will be reported separately, if conducted.

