### 3 ENDPOINTS

#### 3.1 Pharmacokinetic Endpoints

For Part 1 (single ascending dose including assessment of food effect), serial blood samples will be collected pre-dose and post-dose through 28 days to determine concentrations of TBAJ-876 and its metabolites (M2 and M3) in plasma. Additional samples were collected on Days 42, 56, and 70 for Cohorts 4, 5, and 6. For cohort 7, additional samples were only collected on Day 14. Noncompartmental pharmacokinetic parameters of  $AUC_{last}$ ,  $AUC_{inf}$ ,  $C_{max}$ ,  $T_{max}$ ,  $C_{last}$ ,  $T_{last}$ ,  $AUC_{Extrap\%}$ ,  $\lambda_z$ , and  $t_{1/2}$  will be calculated from plasma concentrations of TBAJ-876 (parent), M2 (metabolite), and M3 (metabolite);  $CL/F$  and  $V_z/F$  will be calculated for TBAJ-876 only.

For Part 2 (multiple ascending dose), serial blood samples will be collected pre-dose and post-dose through 24 hours on study days 1 and 14 to determine concentrations of TBAJ-876 and its metabolites (M2 and M3) in plasma. Predose trough plasma samples will be drawn daily Days 1 through 14.

For Part 2 on study day 1, noncompartmental pharmacokinetic parameters of  $AUC_{last}$ ,  $C_{max}$ ,  $T_{max}$ ,  $C_{last}$ ,  $T_{last}$ ,  $AUC_{tau}$ ,  $\lambda_z$ ,  $t_{1/2}$ , and  $C_{24}$  will be calculated from plasma concentrations of TBAJ-876 (parent), M2 (metabolite), and M3 (metabolite);  $CL/F$  and  $V_z/F$  may be calculated for TBAJ-876 if reasonable.

For Part 2 on study day 14, noncompartmental pharmacokinetic parameters of  $AUC_{tau}$ ,  $C_{max}$ ,  $T_{max}$ ,  $C_{min}$ ,  $C_{trough}$ ,  $C_{avg}$ ,  $C_{24}$ ,  $RAUC$ ,  $R_{C24}$ , and  $R_{Cmax}$  will be calculated from plasma concentrations of TBAJ-876 (parent), M2 (metabolite), and M3 (metabolite);  $CL_{ss}/F$  and  $V_z/F$  will be calculated for TBAJ-876 only. Parameters such as  $\lambda_z$ , and  $t_{1/2}$  may be calculated as reasonable.

For Part 3 (relative bioavailability [RBA] including assessment of food effect [FE]), serial blood samples will be collected pre-dose and post-dose through 14 days to determine concentrations of TBAJ-876 and its metabolites (M2 and M3) in plasma. Noncompartmental pharmacokinetic

QMD Ref: Worldwide-TMP-ST-006-4.0 Effective: 12Aug2019	Governing QMD: Worldwide-SOP-ST-001
Confidentiality Statement	

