### 6.2.12.1 Part 1 PK Parameters

The following PK parameters will be calculated for TBAJ-876, M2, and M3 for Part 1:

Parameter	Definition
C max	Maximum plasma concentration, determined directly from individual concentration-time data
T max	Time of the maximum plasma concentrations
C last	Last quantifiable plasma concentration determined directly from individual concentration-time data
T last	Time of last quantifiable plasma concentration
AUC last	Area under the plasma concentration-time curve from time-zero to the time of the last quantifiable concentration (C last ), as calculated by the linear trapezoidal method
AUC 0-24h	Area under the plasma concentration-time curve from time-zero to 24 h postdose, as calculated by the linear trapezoidal method
AUC 0-72h	Area under the plasma concentration-time curve from time-zero to 72 hours postdose, as calculated by the linear trapezoidal method
AUC inf	Area under the plasma concentration-time curve from the time of dosing extrapolated to infinity, calculated as:  AUC inf = AUC last + C last /λ z , where λ z is the apparent terminal elimination rate constant calculated by linear regression of the terminal linear portion of the log concentration versus time curve
AUC Extrap	The percentage of AUC inf based on extrapolation, calculated as:

QMD Ref: Worldwide-TMP-ST-006-4.0 Effective: 12Aug2019	Governing QMD: Worldwide-SOP-ST-001
Confidentiality Statement	

This document is the property of Worldwide Clinical Trials Inc. and may not be duplicated, copied, altered or removed from company without prior approval from Worldwide Quality Assurance or in compliance with Worldwide Standard Operating Procedures.

Worldwide Clinical Trials Controlled Quality Management Document					
 WORLDWIDE CLINICAL TRIALS	Sponsor:	Global Alliance for TB Drug Development			
Protocol Number: TBAJ-876-CL001					
STATISTICAL ANALYSIS PLAN – PHASE 1					

Parameter	Definition
	$(1 - \text{AUC}_{\text{last}}/\text{AUC}_{\text{inf}}) * 100$ (see additional criteria in Section 6.2.12.3)

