### 6.2.12.2.2 Study Day 14 PK Parameters (Part 2)

The following PK parameters will be calculated for TBAJ-876, M2, and M3 for Part 2 (Day 14):

Parameter	Definition
$C_{\max}$	Maximum plasma concentration, determined directly from individual concentration-time data
$T_{\max}$	Time of the maximum plasma concentrations
$C_{\min}$	Minimum plasma concentration, determined directly from individual concentration-time data
$AUC_{\text{tau}}$	Area under the plasma concentration-time curve over the 24 hour dosing interval, calculated using the linear trapezoidal rule
$C_{\text{avg}}$	Average plasma concentration over 24 hours
$C_{24}$	Plasma concentration at 24 hours postdose
$C_{\text{trough}}$	Predose plasma concentration, (Days 2-14)
$\lambda_z$ ( $K_{\text{el}}$ , Lambda z)	The apparent elimination rate constant $\lambda_z$ will be calculated as the negative of the slope of the linear regression through the terminal log-linear segment of the plasma concentration-time curve; the range of data to be used will be determined by visual inspection of a semi-logarithmic plot of concentration vs. time  (see additional criteria in Section 6.2.12.3)  (may be calculated as reasonable)
$t_{1/2}$	The observed terminal elimination half-life, calculated as: $t_{1/2} = \ln(2)/\lambda_z$ (may be calculated as reasonable)
$CL_{\text{ss}}/F$	The apparent total plasma clearance after an oral dose at steady-state, calculated as:

QMD Ref: Worldwide-TMP-ST-006-4.0 Effective: 12Aug2019	Governing QMD: Worldwide-SOP-ST-001
Confidentiality Statement	

This document is the property of Worldwide Clinical Trials Inc. and may not be duplicated, copied, altered or removed from company without prior approval from Worldwide Quality Assurance or in compliance with Worldwide Standard Operating Procedures.

Worldwide Clinical Trials Controlled Quality Management Document					
 WORLDWIDE CLINICAL TRIALS	Sponsor:	Global Alliance for TB Drug Development			
Protocol Number: TBAJ-876-CL001					
STATISTICAL ANALYSIS PLAN – PHASE 1					

Parameter	Definition
	CLss/F=Dose/AUC tau , where F is the bioavailability (calculated for parent only)
Vz/F	The apparent volume of distribution after an oral dose at steady-state, calculated as: Vz/F=Dose/(AUC inf x λ z ), where F is the bioavailability (calculated for parent only)
R AUC	Accumulation ratio of AUC tau for Day 14, calculated as: AUC tau (Day 14)/AUC tau (Day 1)

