#### **6.2.12.4 Lambda-z ( $\lambda_z$ ) Acceptance and AUCinf Reporting Criteria**

The following criteria will be used to report lambda-z and related parameters:

- At least 3 quantifiable concentration-time points should be used in the regression
- Cmax or data prior to Cmax should not be included in the regression
- Adjusted R^2 should be  $\geq 0.8000$

If these acceptance criteria are not met, lambda-z and descriptive parameters such as the time range for the regression, adjusted R^2, etc. will be retained in a parameter listing for informational purposes. Lambda-z will be excluded from summary statistics and from subsequent PK calculations; parameters calculated using lambda-z (e.g. t1/2, AUCinf, CL/F, and Vz/F) will be reported as ND (not determinable).

If lambda-z acceptance criteria are met and AUCinf is estimable, the following criteria are used to report AUCinf:

- The percentage of AUCinf based on extrapolation should be  $<20.0\%$ .

If the percentage of AUCinf based on extrapolation is 20.0% or greater, AUCinf and AUCExtrap will be retained in a PK parameter listing for informational purposes; these parameters will be excluded from summary statistics, subsequent PK calculations (e.g., CL/F, Vz/F), and statistical analysis (e.g. ANOVA).

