14.4.26	Dose Proportionality Plot for TBAJ-876, M2, and M3 $C_{max}$ Following Single Dose Administrations of TBAJ-876 under Fasted Conditions (Part 1; Cohorts 1-7)	IP	
14.4.27	Dose Proportionality Plot for TBAJ-876, M2, and M3 $AUC_{0-24h}$ Following Single Dose Administrations of TBAJ-876 under Fasted Conditions (Part 1; Cohorts 1-7)	IP	
14.4.28	Dose Proportionality Plot for TBAJ-876, M2, and M3 $AUC_{0-72h}$ Following Single Dose Administrations of TBAJ-876 under Fasted Conditions (Part 1; Cohorts 1-7)	IP	
14.4.29	Dose Proportionality Plot for TBAJ-876, M2, and M3 $C_{max}$ Following Single Dose Administrations of TBAJ-876 under Fasted Conditions (Part 2; Cohorts 1-3, Day 1)	IP	
14.4.30	Dose Proportionality Plot for TBAJ-876, M2, and M3 $AUC_{tau}$ Following Single Dose Administrations of TBAJ-876 under Fasted Conditions (Part 2; Cohorts 1-3, Day 1)	IP	
14.4.31	Dose Proportionality Plot for TBAJ-876, M2, and M3 $C_{max}$ Following Single Dose Administrations of TBAJ-876 under Fasted Conditions (Part 2; Cohorts 1-3, Day 14)	IP	
14.4.32	Dose Proportionality Plot for TBAJ-876, M2, and M3 $AUC_{tau}$ Following Single Dose Administrations of TBAJ-876 under Fasted Conditions (Part 2; Cohorts 1-3, Day 14)	IP	
14.4.33	Dose Proportionality Plot for TBAJ-876, M2, and M3 $AUC_{last}$ Following Single Dose Administrations of TBAJ-876 under Fasted Conditions (Part 2; Cohorts 1-3, Day 14)	IP	
14.4.34	Dose Proportionality Plot for TBAJ-876, M2, and M3 $AUC_{inf}$ Following Single Dose Administrations of TBAJ-876 under Fasted Conditions (Part 2; Cohorts 1-3, Day 14)	IP	

QMD Ref: Worldwide-TMP-ST-006-4.0 Effective: 12Aug2019	Governing QMD: Worldwide-SOP-ST-001
Confidentiality Statement	

This document is the property of Worldwide Clinical Trials Inc. and may not be duplicated, copied, altered or removed from company without prior approval from Worldwide Quality Assurance or in compliance with Worldwide Standard Operating Procedures.

Worldwide Clinical Trials Controlled Quality Management Document			
 WORLDWIDE CLINICAL TRIALS	Sponsor:	Global Alliance for TB Drug Development	
	Protocol Number:	TBAJ-876-CL001	
STATISTICAL ANALYSIS PLAN – PHASE 1			

Listing Number	Listing Title	Validation Method	Shell Number (if repeat)
16.2	Subject Data Listings		
16.2.1	Discontinued Subjects		
16.2.1.1	Subject Disposition – All Enrolled Subjects	IP	
16.2.2	Protocol Deviations		

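### Minor: the Part 2 Day 14 Vz/F formula divides one dose by an area that also holds drug from 13 earlier doses, so any value computed from it is several-fold too small

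*SAP*

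**What the plan says.** - **Day 14 volume (SAP 6.2.12.2.2):** "The apparent volume of distribution after an oral dose at steady-state, calculated as: Vz/F=Dose/(AUC inf x λ z"). The same expression is used for single doses in Part 1, Part 2 Day 1 and Part 3.
- **Day 14 clearance, the row above:** "CLss/F=Dose/AUC tau , where F is the bioavailability".
- **AUCinf:** SAP 6.2.12.1 defines it as "Area under the plasma concentration-time curve from the time of dosing extrapolated to infinity, calculated as" AUClast + Clast/lambda-z, with no adjustment for drug already present. The Part 3 table repeats this. AUCinf is not in the Day 14 list. Protocol 9.2 limits its scope: "Area under the concentration-time curve from time-zero extrapolated to infinity; calculated for Parts 1 and 3 as" the same sum.
- **Lambda-z on Day 14 (SAP 3.1):** it and the half-life "may be calculated as reasonable", although CLss/F and Vz/F are planned for the parent without that qualifier.
- **Reporting rule (SAP 6.2.12.4):** "If the percentage of AUC inf based on extrapolation is 20.0% or greater", AUCinf is only listed and is not carried into Vz/F.
- **Dose proportionality:** SAP 6.10 names Cmax, AUClast, AUC0-24h, AUC0-72h and AUCinf for Part 1, but only Cmax and AUCtau for Part 2 Day 14. SAP section 9 nevertheless lists Figures 14.4.33 (AUClast) and 14.4.34 (AUCinf) as Part 2 Day 14 plots, with titles that say single dose and fasted.

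**The concern.** Dose/(AUCinf x lambda-z) works after a single dose because all the drug under the curve came from that dose. After 14 daily doses it did not. The written formula credits one dose with exposure produced by up to 14, so the volume shrinks as carry-over grows. The two adjacent Day 14 rows also cannot both hold: a terminal-phase volume should equal clearance divided by lambda-z, and here the two rows use different areas.

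At stake is how one line of Table 14.4.9.1 is read. A Day 14 Vz/F several-fold below the single-dose value could be taken as a change in distribution on repeated dosing. The like-for-like comparison is the Part 1 100 mg fed group, because Part 2 is dosed fed and the ascending-dose cohorts of Part 1 were fasted.

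**Working it through.** The documents state no Vz/F value or bias factor, so there is no planned figure to reproduce. As a check on the inputs, the parent AUC multiples in Protocol Table 1 follow from the predicted exposures: 26.9/2.1 = 12.8 (stated 13) and 26.9/10.4 = 2.6 (stated 3).

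**Inputs**
- 14 daily doses, so 13 precede the Day 14 dose (Protocol 3, Part 2).
- Planning terminal half-life about 7 days (Protocol 3, Part 1).
- Predicted parent AUC0-24h: 2.1 on Day 28 of 25 mg daily, and 10.4 after a single 400 mg dose (Protocol 1.4, notes to Table 1).
- Assumed: linear kinetics, dose proportionality from 400 to 25 mg, and the fast-phase half-lives below.

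**Formula.** Let h be the half-life in days and r = 2^(-1/h). By superposition, for one exponential phase:
- factor by which Vz/F is too small = (AUC from dose 14 to infinity)/(single-dose AUCinf) = (1 - r^14)/(1 - r);
- Day 14 AUCtau/(single-dose AUCinf) = 1 - r^14.

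For two phases, each result is the average over the phases, weighted by each phase's share of single-dose AUCinf.

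**One compartment, 7 days.** r^14 = 2^-2 = 0.25 and 1 - r = 0.0943. Factor = 0.75/0.0943 = 8.0.

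**Matched to the predicted exposures.** Implied Day 28 accumulation = 2.1/(10.4 x 25/400) = 2.1/0.65 = 3.23.
- *Mono-exponential:* (1 - r^28)/(1 - r) = 3.23 gives h = 1.87 days. Factor 3.2.
- *Two-phase, 7-day terminal half-life, fast half-life 0.1 day (assumed):* the terminal phase must carry 0.78 of AUCinf. Factor = 0.779 x 7.96 + 0.221 x 1.00 = 6.4.
- *Same, fast half-life 1.0 day (assumed):* terminal share 0.49. Factor = 0.493 x 7.96 + 0.507 x 2.00 = 4.9.
- *Two-phase, terminal half-life 14 to 28 days (assumed):* 6.2 to 10.2.

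**With the SAP sampling times and linear trapezoid.** Using the true lambda-z, bolus input and all samples quantifiable, the first three cases become 9.3 (one compartment, 7 days), 3.9 (mono-exponential) and 5.7 to 7.5 (two-phase, 7 days). The rise comes mainly from the single trapezoid between 168 h and Day 42.

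**Gap between the two Day 14 rows.** (CLss/F)/lambda-z divided by the written Vz/F is AUCinf/AUCtau, both from the Day 14 dose: 3.21/0.994 = 3.2 (mono-exponential), 4.94/0.877 = 5.6 to 6.42/0.805 = 8.0 (two-phase, 7 days), and 7.96/0.75 = 10.6 (one compartment, 7 days).

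**Does the 20% rule catch it?** The rule tests extrapolation, not carry-over. For one compartment the extrapolated share is 2^(-t/h), with t the days from dose 14 to the last quantifiable sample. At 7 days it is 0.002% if that sample is Day 126 (t = 112), 6% if Day 42 (t = 28), and 50% if 168 h (t = 7). The biased value passes in the first two cases and is withheld in the third. The documents give no limit of quantitation, so which applies is unknown.

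**Residual bias of Dose/(AUCtau x lambda-z).** This form is exact only at steady state. Protocol 1.7 predicts daily AUCs rising through Day 14. The overestimate is the reciprocal of Day 14 AUCtau/AUCinf: 1/0.75 = 1.33 (one compartment, 7 days), 1/0.877 = 1.14 to 1/0.805 = 1.24 (two-phase, 7 days), 1/0.50 = 2.0 (one compartment, 14 days), and about 2.5 at most for the matched two-phase models at 28 days.

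**The case against.** **AUCinf is not specified for Day 14.** It is missing from the Day 14 list, and the protocol confines it to Parts 1 and 3. A too-small value therefore arises only if someone computes AUCinf from the Day 14 dose uncorrected. The SAP's amendment list shows a deleted Day 28 set that held AUCinf, CLss/F and Vz/F together, so the row may be a leftover (an inference). This supports calling it an editing slip. It does not rescue the formula: followed literally it is wrong, and read otherwise it has no defined input.

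**The impact is small.** This stands. Vz/F enters no test or comparison, the dose rationale in Protocol 1.7 rests on model-predicted AUCs, and a correct value can be recomputed from CLss/F and lambda-z without new data.

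**A reader might infer a narrow range, such as 3 to 6-fold.** The documents do not support one. The low end needs a 1.87-day half-life, against a 7-day planning value and multiexponential disposition in animals (Protocol 1.5). The upper end would cap the terminal half-life at 7 days and set aside the 8.0-fold one-compartment case and the sampling effect. The matching also uses planning predictions and assumed dose-linearity.

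**A reader might infer that every subject's value will be wrong, or that Figures 14.4.33 and 14.4.34 should be deleted.** Neither follows. Vz/F needs an optional lambda-z and can be withheld under the 20% rule. SAP 6.10 plans AUClast and AUCinf for Part 1, yet Figures 14.4.26 to 14.4.28 cover only Cmax, AUC0-24h and AUC0-72h. The two figures may be mislabelled Part 1 plots.

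**Conclusion.** The Day 14 Vz/F formula is wrong as written, and the fault is minor. Under linear kinetics the direction is certain: any value computed this way is too small and disagrees with the CLss/F row. The size is several-fold but not known: 3.2, 4.9 to 6.4, or 8.0 across the three main cases, up to about 10 for matched models with assumed longer terminal half-lives, and somewhat higher with the SAP's sampling times and trapezoidal rule. The matched figures assume dose proportionality from 400 to 25 mg and rest on predicted, not observed, exposures.

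The effect is confined to one secondary, descriptive, parent-only parameter, where lambda-z is reported. Cmax, AUCtau, the analyses in SAP 6.10 and safety are untouched. A reader might infer a threat to dose escalation or to the dose-proportionality conclusions; nothing in the documents feeds Day 14 Vz/F into either.

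**What to change.** 1. In SAP 6.2.12.2.2, define Day 14 Vz/F = Dose/(AUCtau x lambda-z) = (CLss/F)/lambda-z, with lambda-z from the washout after the Day 14 dose.
2. Label Day 14 CLss/F and Vz/F as apparent values, and state that both are too large if steady state is not reached: about 1.1 to 1.3-fold at a 7-day terminal half-life, and 2-fold or more if it is much longer.
3. Reconcile the titles and content of Figures 14.4.33 and 14.4.34 with SAP 6.10: either relabel them as Part 1 plots, or justify AUClast and AUCinf for Part 2 Day 14. Do not simply delete them.

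Cost: one formula row, one sentence, two figure entries and a small programming change. No new samples.

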#### 6.2.12.3 Part 3 PK Parameters

The following PK parameters will be calculated for TBAJ-876, M2, and M3 for Part 3:

Parameter	Definition
C max	Maximum plasma concentration, determined directly from individual concentration-time data
T max	Time of the maximum plasma concentrations
C last	Last quantifiable plasma concentration determined directly from individual concentration-time data
T last	Time of last quantifiable plasma concentration

QMD Ref: Worldwide-TMP-ST-006-4.0 Effective: 12Aug2019	Governing QMD: Worldwide-SOP-ST-001
Confidentiality Statement	
This document is the property of Worldwide Clinical Trials Inc. and may not be duplicated, copied, altered or removed from company without prior approval from Worldwide Quality Assurance or in compliance with Worldwide Standard Operating Procedures.	

Worldwide Clinical Trials Controlled Quality Management Document					
 WORLDWIDE CLINICAL TRIALS	Sponsor:	Global Alliance for TB Drug Development			
Protocol Number: TBAJ-876-CL001					
STATISTICAL ANALYSIS PLAN – PHASE 1					

Parameter	Definition
AUC 0-24h	Area under the plasma concentration-time curve from time-zero to 24 h postdose, as calculated by the linear trapezoidal method
AUC last	Area under the plasma concentration-time curve from time-zero to the time of the last quantifiable concentration (C last ), as calculated by the linear trapezoidal method
AUC inf	Area under the plasma concentration-time curve from the time of dosing extrapolated to infinity, calculated as: $AUC_{inf} = AUC_{last} + C_{last}/\lambda_z$ where $\lambda_z$ is the apparent terminal elimination rate constant calculated by linear regression of the terminal linear portion of the log concentration versus time curve
AUC Extrap	The percentage of AUC inf based on extrapolation, calculated as: $(1 - AUC_{last}/AUC_{inf}) * 100$ (see additional criteria in Section 6.2.12.4)
$\lambda_z$ (K el , Lambda z)	The apparent elimination rate constant $\lambda_z$ will be calculated as the negative of the slope of the linear regression through the terminal log-linear segment of the plasma concentration-time curve; the range of data to be used will be determined by visual inspection of a semi-logarithmic plot of concentration vs. time (see additional criteria in Section 6.2.12.4)
t 1/2	The observed terminal elimination half-life, calculated as: $t_{1/2} = \ln(2)/\lambda_z$
CL/F	The apparent total plasma clearance after an oral dose, calculated as : $CL/F = Dose/AUC_{inf}$ , where F is the bioavailability (calculated for parent only)

QMD Ref: Worldwide-TMP-ST-006-4.0 Effective: 12Aug2019	Governing QMD: Worldwide-SOP-ST-001
Confidentiality Statement	

This document is the property of Worldwide Clinical Trials Inc. and may not be duplicated, copied, altered or removed from company without prior approval from Worldwide Quality Assurance or in compliance with Worldwide Standard Operating Procedures.

Worldwide Clinical Trials Controlled Quality Management Document					
 WORLDWIDE CLINICAL TRIALS	Sponsor:	Global Alliance for TB Drug Development			
Protocol Number: TBAJ-876-CL001					
STATISTICAL ANALYSIS PLAN – PHASE 1					

Parameter	Definition
Vz/F	The apparent volume of distribution after an oral dose, calculated as: Vz/F=Dose/(AUC inf x λ z ), where F is the bioavailability (calculated for parent only)

